APPENDIX II- Technical Frailty Index (CIFI)

Technical Frailty Index will be constructed according to the fine-tuning of the FrailSafe system that we are going to achieve during the initial period of the field studies (groups A and B). Although its distinct components are going to be evaluated separately, it will be fully used as a composed index in a later phase of the study (experimentation period for group C).

The main components from which it is going to be constructed are presented in general terms in table 23.

Measurements	High level data	Frequency
Heart Rate	 Mean value when sitting Mean value when sleeping Mean value when walking Mean value when lying Mean value when walking upstairs and downstairs 	for each day - sampling every 5sec (250 Hz)
Respiration Rate	 Mean value when sitting Mean value when sleeping Mean value when walking Mean value when lying Mean value when walking upstairs and downstairs 	for each day - sampling every 15sec (25 Hz)
Walking	 Number of steps Number of walking activity initiation Mean duration of the walking activity 	for each day sampling (25 Hz)
Posture	 Mean time spent standing/day Mean time spent sitting/day Mean time spent lying/day 	for each day
Instability/Falls	 Falls rate Almost/failed falls rate Places where falls/almost falls happen (indoors/outdoors) - what type of activity performed Fall consequences Physiological state of the subject one minute before Number of fear of fall instances 	
Strength	Mean max strength value	for each block
Blood Pressure	Mean value when sittingMean value when standing	for each day sampling (3 times)
Game Analysis	 Played the game? Number of times/block Success rate Mean reaction time Mean Duration Mean Time of pauses Number of pauses/block Events triggered Concentration index 	for each block

Table 23. Components to contribute to the generation of Technical Frailty Index

Indoor Activities	 Mean time spent sitting in the living room Mean time spent lying in bed Mean time spent in the restroom Mean time spent walking inside Mean time spent using tablet/pc 	for each day
Outdoor Activities	 Mean time spent walking outside Mean time spent driving car Mean time spent riding bike Mean time spent carrying things (e.g. shopping bags) 	for each day

5.3 Hypothesis Generation

According to outcomes and Frailty Indices definitions, the medical objectives of the study can be operationally approached as described in table 24.

Table 24. Hypothesis Generation for the analysis of data per MO

M01.	(Understanding frailty and relation to co-morbidities)
	What is the relation of most prevalent comorbidities with Clinical Frailty Index and with proxy and hard outcomes.
MO2	(Develop quantitative and qualitative measures to define frailty)
	Assess the ability of the Technical Frailty Index to describe reduced reserves, as expressed by Clinical Frailty Index and proxy and hard outcomes
MO3	(Use these measures to predict short and long-term outcome)
	Evaluate the ability of each component of the Clinical or Technical Frailty Indices, and/or combination of those, to predict Proxy and Hard Outcomes
MO4	(Develop real life tools for the assessment of physiological reserve and external challenges)
	Identify the influence of each component of the Combined Frailty Index to best predict proxy and hard outcomes, in order to validate the predictive value of the Combined Frailty Index.
M05	(Provide a model sensitive to change)
	Identify the sensitivity of each component of the Combined Frailty Index to describe shift in reserve as a holistic measure defined by the proxy and hard outcomes
MO6	(Create "prevent-frailty" evidence based recommendations)
	Assess if positive attitude or changes, that took place in each and every aspect of the frailty sub-indices, contribute to a modification of the expected patterns

	of the proxy and hard outcomes, so as to be proposed as clinical recommendations
	For example, a recommendation could be provided for physical, cognitive or social actions, which have been tested during the study and have shown a positive profile in regards of proxy and hard outcomes.
M07	(Achieve all with a safe and acceptable to older people system)
	Constantly evaluate and record the acceptability and safety aspect of the FrailSafe system application and the totality of the procedures followed during the study.

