The sample was recruited after specifying lower age limits and certain comorbidities. The intention which was described and accepted in the initial proposal, was to include certain key comorbidities, which are in a relatively low prevalence in elderly population. Otherwise, these comorbidities would have been under representative in our small sample, and their effect on frailty process might have been lost. These comorbidities, among many others equally important, may accelerate the frailty process; they may also influence the scoring of frailty according to Fried's criteria. For instance a previous stroke or the presence of osteoarthritis may slow down the speed of walking altering the frailty score, whilst at the same time would not contribute to a functional worsening in time. Mild cognitive impairment may have an opposite effect, as it does not directly modify the Fried frailty score, but may strongly influence the loss of functional reserve.

During clinical evaluation, together with the pre-specified comorbidities, up to twenty seven other possible medical conditions/comorbidities are also recorded. Thus, the analysis of data regarding comorbidities will not be carried out exclusively around the pre-specified ones. The absolute number of accumulated comorbidities, the absolute number of the most prevalent comorbidities, and a choice of the most prevalent comorbidities will be explored as independent or confounding factors to the frailty process. An effect on functional change may be shown by adding or subtracting groups of individuals with common comorbidity/ies.

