APPENDIX I- Clinical Frailty Index (CIFI)

We define loss of physiological reserve changes in ten domains investigated by the clinical evaluation assessment (health status, physical performance, nutritional, cognitive, psychological, wellness etc). We add up scores from all variables in order to have an initial rough index that expresses frailty parameters altogether. Due to lack of sufficient data in the literature about the specific weight of each item and even of each domain, we have chosen to initially take equal weights for each item, aiming at validating our model in the end of the study in terms of frailty evolution predictive value, as expressed by outcomes occurrence.

Items that will contribute to the generation of the CIFI are listed in table 22.

Table 22. Components of Clinical Frailty Index

Items	
Medical Domain (M)	Each polypathology /Comorbidities (M)
	Comorbidity's impact (M, P, s, c)
	Polymedication (M, p, c)
	Orthostatic hypotension (M, p)
	Visual impairment (M, S, p)
	Hearing impairment (m, S, c)
General Condition	Unintentional weight loss (M, ψ)
Domain (Μ, ψ)	Self-reported exhaustion (M, ψ)
Physical Condition	Balance (single foot standing) (P, m)
(P, m, c)	Gait-related task speed* (P, c)
	(Timed Get Up and Go test)
	Gait - speed 4 m (P, m)
	Lower limb strength (P, m)
	Grip strength –dynamometer (P, m)
	Qualitative evaluation of mobility (P, m)
	Low physical activity (P, M, s, ψ)
Nutrition (M, Ψ , c, s)	Too low BMI (Μ, Ψ, p, c, s)
	Too high BMI (M, Ψ, Ρ, ϲ, s)
	Waist circumference (M, Ψ , P, c, s)
	Lean body mass (M, P, ψ)
	Total MNA score (M, Ψ, p, c, s)
Cognitive Domain	MMSE scores (C, ψ , m)
(C, ψ, m, s)	MoCA score(C, ψ, m)
	Subjective memory complaint(C, ψ , m, s)
	Natural language analysis (C, Ψ)
Psychological Domain	GDS-15*(Ψ, S, c)
(Ψ, S, c)	Self-rated anxiety (Ψ, S, c)
	Natural language analysis (C, Ψ)
Social Domain (S, Ψ , m)	Living conditions (S, Ψ , p, m)

Social Domain (S, Ψ, m)	Leisure activities (S, Ψ , p, m)			
	Membership of a club (S, Ψ , p, m)			
	Number of visits and social interactions per week (S, Ψ , p, m)			
	Number of telephone calls exchanged per week (S, ψ , m)			
	Approximate time spent on phone per week (S, ψ , m)			
	Approximate time spent on videoconference per week (S, ψ)			
	Number of written messages sent by the participant per week (S, ψ , m, p)			
Environmental Domain	Subjective suitability of the housing environment according to			
(S, P, m)	participant's evaluation (S, P, m)			

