Annex 1- COMORBIDITIES' LIST

(SELF-REPPORTED BY THE PARTICIPANTS AND REVEALED BY THEIR MEDICATION LIST)

COMORBIDITIES	Check if the condition is present	Check if you think that the condition affects significantly the person's functional status
ARTERIAL HYPERTENSION		
DYSLIPIDEMIA		
DIABETES MELLITUS		
ISCHEMIC HEART DISEASE		
CHRONIC ATRIAL FIBRILLATION/PAROXYSMAL AF OR OTHER ARRYTHMIA		
HEART INSUFFICIENCY		
STROKE OR TIA		
CHRONIC RENAL DISEASE		
RESPIRATORY DISEASE		
CANCER		
IMPAIRED COGNITIVE FUNCTION		
PARKINSON'S DISEASE		
EPILEPSY		
DEPRESSIVE EMOTION		
ANXIETY AND/OR SLEEP PROBLEM		
URINARY INCONTINENCE		
PROSTATE PATHOLOGY		
ANEMIA		
ARTHRALGIES- MUSCULOSCELETAL COMPLAINTS/DISEASES		

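### MO1 relates comorbidities to a Clinical Frailty Index that already counts them, so part of that association is built in

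*Protocol*

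**What the plan says.** Section 5.3, Table 24, asks under MO1: "What is the relation of most prevalent comorbidities with Clinical Frailty Index and with proxy and hard outcomes". The exposure is a comorbidity, and there are three kinds of outcome: CIFI, proxy outcomes and hard outcomes.

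Appendix I defines CIFI. The Medical Domain of Table 22 opens with "Each polypathology /Comorbidities (M" and "Comorbidity's impact (M, P, s, c" (the letters in brackets are the table's domain tags). The scoring rule is "We add up scores from all variables in order to have an initial rough index that expresses frailty parameters altogether", and on weighting, "we have chosen to initially take equal weights for each item".

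Annex 1 gives each listed condition two boxes. One is for presence. The other carries the instruction "Check if you think that the condition affects significantly the person's functional status". Section 2.4 says that, besides the pre-specified conditions, "up to twenty seven other possible medical conditions/comorbidities are also recorded". It also plans to explore the number of accumulated comorbidities as a factor in the frailty process. Section 5.4.2 expects that grouping equivalent comorbidities will help statistical significance.

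No section defines a CIFI without the comorbidity items for MO1, and none mentions this overlap.

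**The concern.** If a comorbidity is one of the terms added up to form CIFI, people who have it score higher on CIFI for that reason alone. An association between the two then mixes a bookkeeping effect with whatever real relation exists, and the analysis as written cannot separate them. More participants do not help. The built-in part stays the same size and becomes easier to detect.

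The effect is also uneven. A condition that is often flagged for impact contributes more than one that is not. Some conditions are measured again by other items, for example impaired cognition by MMSE and MoCA, or depressive mood by GDS. A ranking of conditions by their association with CIFI would partly reflect how many items each one feeds.

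Understanding frailty and its relation to comorbidities heads the list of objectives in section 2.1, so this is not a side analysis.

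**Working it through.** The protocol gives no sample size, significance level or expected effect for MO1, so there is no figure of its own to reproduce.

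**Structure.** For one condition with presence C (0/1) and impact flag I (0/1, possible only when C = 1), the additive, equally weighted index is CIFI = C + I + R, where R is the sum of all other items. If C is unrelated to R, carriers and non-carriers still differ in mean CIFI by 1 + P(I = 1 | C = 1). That is 1 point if no carrier is flagged, 1.5 if half are, and 2 if all are.

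**Inputs.**
- From the documents: 360 participants in groups A and B (3 centres × 120), and 510 in all.
- Assumed, because the documents do not give them: 0/1 scoring, condition prevalence 30–50%, CIFI SD 6 (range 4–8), two-sided 0.05.

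**Rejection probability with no true relation to R.** With d = overlap/SD and z = d/√(1/n₁ + 1/n₀), the probability is Φ(z − 1.96) + Φ(−z − 1.96).

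Example: N = 360, prevalence 30% (108 carriers, 252 others), one point, SD 6. Then d = 0.167, √(1/108 + 1/252) = 0.115, z = 1.449, and the probability is 31%.

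| Overlap | N = 360, SD 6 | N = 360, SD 8 to 4 | N = 510, SD 6 |
|---|---|---|---|
| 1 point (no carrier flagged) | 31–35% | 19–66% | 41–47% |
| 1.5 points (half flagged) | 58–66% | 37–94% | 73–81% |
| 2 points (every carrier flagged) | 83–89% | 58–100% | 93–96% |

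**Simulation.** All items were independent: 27 binary comorbidities (prevalence 10–50%) and 44 other 0/1 items (prevalence 30%), 2,000 runs per setting.
- Comorbidity items only: mean correlation 0.09–0.13; rejection 39–68% at N = 360 and 49–81% at N = 510.
- Half of carriers also flagged for impact: rejection 59–79% at N = 360 and 73–90% at N = 510.
- Tested condition and its impact item removed from the index: rejection about 4–6%.
- All comorbidities rescaled to one 0–1 proportion, and likewise impact: correlation about 0.01, rejection about 4–6%.

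These rates lie above the SD 6 figures because independent 0/1 items imply a smaller SD. At 30% prevalence it is √(71 × 0.3 × 0.7) = √14.91 = 3.9, at the low end of the assumed range.

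**Counts and groups.** With the same independent items and no impact items, the built-in correlation of a sum of k comorbidities with CIFI is √(k·p(1 − p)/Var(CIFI)).
- At p = 30%, Var = 14.91: all 27 give √(5.67/14.91) = 0.62; a group of five gives √(1.05/14.91) = 0.27.
- At p = 10%, Var = 27 × 0.09 + 44 × 0.21 = 11.67: the values are √(2.43/11.67) = 0.46 and √(0.45/11.67) = 0.20.

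In simulation at N = 360 the count was significant in every run, and the group of five in 97–100% of runs.

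**The case against.** Several points on the other side are fair.

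- **Other outcomes.** A reader might infer that MO1 as a whole is circular. It is not. The hard outcomes (section 5.2.1) and proxy outcomes (section 5.2.2) do not have comorbidity status as a summand. Some proxies (MoCA/MMSE, GDS) are close in content to listed conditions, but that is a weaker matter.
- **Certainty.** A reader might infer that every comorbidity will come out as significantly related to frailty. The figures do not say so. For the one-point overlap at SD 6 and N = 360, about two thirds of tests would not be significant. What is built in is a positive contribution, which a negative relation with other items could offset.
- **The upper figures.** The 83–89% needs every carrier to be flagged for impact. A condition that clinicians always judge to impair function is hard to describe as unrelated to the rest of frailty, so this is a ceiling.
- **Scoring.** The protocol fixes no item scores. With one rescaled comorbidity item, single-condition inflation nearly vanishes. If items such as MMSE or weekly phone time entered on raw scales, the SD could be much larger; at an assumed SD of 20, one point gives about 7–8%. Item scoring may be settled in an analysis plan not shown here.
- **Context.** The analysis is exploratory and no significance level is stated, so 5% is a benchmark chosen here. Section 5.4.3 plans to look for duplicate and overlapping observations, and section 5.2.3 lists changes in CIFI, from which a stable condition would cancel.

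These points limit the size and scope but do not remove the overlap. The wording of Table 22 and the equal weighting per item favour separate comorbidity items, although they do not settle the scoring. Section 5.4.3 is generic and not tied to MO1, and MO1 does not say that it uses change in CIFI.

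**Conclusion.** The point holds for the CIFI part of MO1. The protocol itself fixes both sides of the conflict, the composition of the index and the hypothesis that uses it, so it does not turn on detail that an analysis plan would normally supply. Each comorbidity has a built-in positive association with CIFI, and a count or group has a stronger one.

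The size is conditional on the assumptions above. Under them, false rejection for a single condition at N = 360 and SD 6 is about 31–35% for a one-point overlap, rising with the share of carriers flagged for impact. Collapsing all comorbidities into one rescaled item would bring it to about 5%. The documents do not support the broader conclusions that MO1 is void or that every condition must appear related to frailty.

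**What to change.** In Table 24, MO1, state that comorbidities are related to a single reduced CIFI that omits all comorbidity and comorbidity-impact items. Use the same reduced index for every condition, so that associations can be compared across conditions and a count or group shares no item with the outcome. Keep the full CIFI for the other objectives, and leave the proxy- and hard-outcome parts of MO1 as they are.

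As a sensitivity analysis, also drop polymedication and the items that measure the condition again (for example MMSE/MoCA for MCI, GDS for depressive mood). This should not be the main analysis: it gives each condition a different index, so results are no longer comparable between conditions, and it may discard real consequences of the condition.

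The cost is a sentence in Table 24 and one extra version of the index from data already collected. Reported associations will be smaller, because the built-in part is gone. The change should be made before MO1 is analysed.

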5.2.2 Proxy outcomes

Due to the limited number of participants, the tight timeframe of the project and the frequency of occurrence of Hard Outcomes, we propose the use of proxy outcomes that we are confident that we will be able to measure and to use in the data analysis part of the project to draw some solid conclusions. The proxy outcomes could also be considered as a diagnostic, early detection tool of a declining condition that may lead to a hard outcome. By keeping a concise, short, practical yet informative track of the change in proxy outcomes we will be able via coaching and interventions to postpone the inevitable occurrence of a Hard outcome, thus improving prognosis and quality of life.

Repeated clinical evaluations are carried out in the following domains: physical, cognitive, psychological, nutritional, and wellness. Loss of function in each domain can indirectly describe loss of physiological reserve, which underscores frailty, and consequently the adverse events of frailty (described above in 5.2.1). The clinical experts of this consortium in a consensus meeting have agreed on a key clinical assessment of each domain, which best describes loss of reserve and is believed to predict adverse outcome.

Therefore, as proxy outcomes have been selected the following:

- Gait speed (Physical Domain)
- MoCA and/or MMSE (Cognitive Domain)
- GDS (Psychological Domain)
- Weight loss (Nutritional Domain)
- Health status self-assessment (General health/Wellness Domain)

The clinicians in the process of selecting a proxy outcome in each domain made use of the bibliography and their expert opinion. At the end of the clinical studies, analysis will be carried out correlating these proxy outcomes to the hard outcomes observed in participants and, if possible, explore validity and reliability.

Review of the bibliography showed that gait speed test has been established as the test with the strongest correlation to frailty (72), and has been linked with the hard outcomes, such as falls and mortality (73,74). Reduced MoCA and MMSE scores, though the later to a lesser extent as less sensitive to the detection of mild cognitive decline, have been linked both with

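### CIFI, CoFI and their components are to be tested against proxy outcomes that they contain; TFI and CoFI overlap with falls in the same way when both cover the same period

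*Protocol*

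**What the plan says.** Section 5.2.2 names five proxy outcomes. Appendix I (Table 22) lists the items that are summed, initially with equal weights, into CIFI. Set side by side (some entries are quoted only up to a bracket):

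- Gait: proxy "Gait speed (Physical Domain"; CIFI item "Gait - speed 4 m (P, m".
- Cognition: proxy "MoCA and/or MMSE (Cognitive Domain"; Table 22 lists both the MMSE and the MoCA score.
- Mood: proxy "GDS (Psychological Domain"; Table 22 lists the GDS-15.
- Weight: proxy "Weight loss (Nutritional Domain"; CIFI item "Unintentional weight loss (M".
- Self-rated health: proxy "Health status self-assessment (General health/Wellness Domain"; Table 22 lists self-rated health under Wellness.

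Section 5.2.1 counts a fall as a hard outcome, and Appendix II (Table 23) lists falls rate and fall consequences among the TFI components. Section 5.1 defines CoFI as CIFI plus TFI.

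In Table 24, MO3 is to "Evaluate the ability of each component of the Clinical or Technical Frailty Indices, and/or combination of those, to predict Proxy and Hard Outcomes". MO4 uses the prediction of proxy and hard outcomes by each CoFI component as the means of validating CoFI. MO5 asks how sensitive each CoFI component is to a shift in reserve that is itself defined by those outcomes. No section takes a shared item out of the index or out of the outcome.

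**The concern.** An index tested against an outcome that is one of its own inputs will agree with it whether or not it carries any other information. Taken literally, MO3 to MO5 include the GDS predicting the GDS and gait speed predicting gait speed.

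Three features of the plan make this matter:

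- Sections 5.2.2 and 5.4.2.3 bring in the proxies because hard outcomes are expected to be few, so much of the validation will rest on the proxies.
- The main objective in 2.1 is the value that the FrailSafe system adds to standard clinical approaches. CIFI contains the proxies and TFI contains none of them, so a comparison of the two on the proxies is tilted towards CIFI.
- Appendix I treats the equal weights as provisional, to be validated against outcomes, and 5.4.2 plans stepwise selection. Selection against a proxy will favour the shared items.

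**Working it through.** The protocol gives no figure to reproduce on this point. The check is a count of the overlap, followed by an illustration of its size.

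**Overlap.** Table 22 has 6 + 2 + 7 + 5 + 4 + 3 + 8 + 3 + 5 + 3 = 46 entries in ten domains.

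- All five proxies (six instruments, since MMSE and MoCA are both listed) have a counterpart there. Weight loss is the one loose match: the clinical item in Table 9 is a self-reported loss of more than 4.5 kg in the past year, and 5.2.2 does not say whether the proxy is that item or a change in measured weight.
- None of the six hard-outcome bullets in 5.2.1 is an entry in Table 22.
- One of the six, the fall, is among the entries of Table 23.

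**Assumptions for the illustration.** CIFI is an equal-weight sum of k standardised, mutually independent items. The documents do not state this. I take k = 46, with a range from 43 (anxiety, natural language analysis and physical activity each counted once instead of twice) to 72 (27 comorbidities counted singly: 46 - 1 + 27). The sample is n = 510 for all participants, or 3 x (80 + 40) = 360 for groups A and B.

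**Same visit.**

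- A component against itself: r = 1.
- The index against one of its items: r = 1/sqrt(k) = 1/sqrt(46) = 0.147. The range is 0.152 (k = 43) to 0.118 (k = 72).
- Fisher z = atanh(0.147) x sqrt(n - 3): 3.34 at n = 510 (p = 0.0008) and 2.81 at n = 360 (p = 0.005).
- In 2,000 simulated data sets of 510 people with unrelated items, 92% gave p < 0.05.
- The index against the sum of the shared instruments: sqrt(6/46) = 0.36, or sqrt(5/46) = 0.33 if weight loss is not counted as shared.
- With the shared item left out of the index, the value under the same assumptions is 0.

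**Earlier index, later proxy level.** Through the shared item alone, r = rho/sqrt(46), with rho the retest correlation (assumed):

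- rho = 0.5: 0.074 (p = 0.096 at n = 510)
- rho = 0.7: 0.103 (p = 0.020)
- rho = 0.9: 0.133 (p = 0.003)

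**Earlier index, later change.** For the item itself, r = -sqrt((1 - rho)/2): -0.50, -0.39 and -0.22 for rho = 0.5, 0.7 and 0.9, and -0.316 for rho = 0.8. For the index, multiply by 0.147. At rho = 0.8 that is 0.147 x -0.316, about -0.05, with z about -1.05 and p about 0.29 at n = 510. At rho = 0.5 it is -0.07, and at rho = 0.9 it is -0.03.

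**Falls.** Section 4 keeps the system in the home for 3 to 5 days, or 60 days in group Cii. Falls as an outcome come from the follow-up questionnaire, about every three months (3.3). Taking 90 days, a session covers 3/90 = 3% to 5/90 = 6% of the window, and 60/90 = 67% in group Cii, which has 5 people per centre. A fall during a session can count both in TFI and in the next questionnaire.

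**The case against.** The strongest reply is that the objectives speak of prediction, and that no section plans to set CIFI against a proxy at the same visit. Section 5.2.2 looks at change in the proxies, gives each trajectory its own starting level, plans lag correlations, and asks what the device variables add to the proxies. On this view 0.15 and 0.36 describe a test that nobody proposed, an earlier value predicting a later one is ordinary autoregression, and leave-out scoring belongs in an analysis plan that is not shown.

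Much of this stands. The same-visit figures apply only to same-visit tests. The device-against-proxy step is sound, and earlier-to-later prediction is not strictly circular. But the lag correlations are stated for device variables, not for CIFI or CoFI, and nothing in Table 24 requires the index to come first or the baseline proxy to be in the model. An earlier index would still borrow about 0.07 to 0.13 from the shared item. Nor is this only a missing detail, because the protocol itself fixes the index content, the outcomes and the hypotheses, and these three conflict.

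The falls overlap is also modest. Outside group Cii the sessions are short, Table 23 is given only in general terms, and a fall in one session followed by a later fall is event history, not circularity.

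**Conclusion.** The point holds for CIFI, CoFI and their components against the five proxies (MO3 to MO5), and for TFI and CoFI against falls when the TFI fall items and the fall outcome cover the same period. The artefact is complete (r = 1) for a component against itself at one visit. For the whole index it is about 0.15 per proxy at one visit and about 0.07 to 0.13 for a later level. The index figures rest on independent, standardised, equally weighted items and on assumed retest correlations. They show that the artefact can reach significance at this sample size; they do not estimate its size in the real data.

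A reader might infer three stronger things that the documents do not support:

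- That predicting hard outcomes is circular in general. CIFI contains no hard outcome, so CIFI against death, hospitalisation, institutionalisation, ADL/IADL decline, fracture or falls is not circular. The Cox step in 5.2.2 is affected only where TFI or CoFI meets falls in the same period.
- That MO2 to MO6 are all affected. MO2 tests TFI, which contains none of the five proxies, so only its falls part overlaps. MO6 concerns changes that might support recommendations, not validation of an index.
- That the link between baseline and change makes an empty index look predictive of decline. It is negative, so it would mask prediction of decline. The -0.32 at rho = 0.8 belongs to the item; for the index it is about -0.05 and would not be detected at n = 510.

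**What to change.** Add to 5.3:

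- For each proxy, recompute CIFI and CoFI without the items that measure it, and do not test a component against itself. List the items proxy by proxy: 4 m gait speed for gait; MMSE and MoCA for cognition; GDS-15 for mood; unintentional weight loss for weight; self-rated health for health status.
- Define the proxies closely enough to apply that list. Table 8 puts the Timed Get Up and Go under gait speed as well, Table 14 has a second health question on change over the year, the MNA in Annex 5 includes a weight-loss question, and the weight-loss proxy needs to be stated as self-reported or measured.
- For falls, recompute TFI and CoFI without the entries that record actual falls, or use only TFI sessions that end before the fall window opens.
- Take index values from an earlier visit than the outcome, include the baseline proxy value in the model, and report performance as the gain over that baseline.
- Use the same rules in any comparison of CIFI with TFI.

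This costs a few lines of text and some code, and needs no new data. The reported predictive performance will look less favourable. It is best settled before the data analysis that 2.6 links to the M27 decision, because a later change would look post hoc.
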